Number of subjects was based on a power analysis using FVC/FEV₁ as the primary variable and stratified by unilateral versus bilateral diagnosis. Previous literature suggests a standard deviation of approximately 0.20-0.60 for FVC/FEV₁ values. SD was set at 0.40. Unilateral control was estimated to be 50% of predicted values (FVC/FEV₁) due to the nature of the injury, set at approximately 1.50L, with bilateral set at approximately 1.35L. Unilateral experimental group means were increased by 20% of predicted values to 1.80L, and bilateral to 1.50L. The required sample size to achieve 80% power to detect difference between splint and control groups is 104, with each group requiring 26 subjects each. Power calculations were performed in R version 4.0.0 with the pwr2ppl package, using the anova2x2 function.

Number of subjects to be used are 150 to account for withdrawals, incomplete data sets, extraneous results, etc. This is a single site study.

7) Recruitment Methods

Respiratory Therapy is part of the trauma multi-disciplinary team. and is involved with the care of every trauma patient admitted to Penrose Hospital. During trauma rounds in the ICU and floor patients that met criteria for the study will be identified. The investigators will approach those identified patients for potential enrollment in the study. Note they will not approach any patient for consent that is under their care that shift. There are no flyers or advertisements for this research or device.

8) Study Timelines

It is estimated that it will take at least one year to complete this study to include enrollment, subject completion, and all analysis. All primary variables and analyses should be completed by this time.

9) Study Endpoints

The primary endpoint of this study is to investigate the use of the Duracore splinting device in patients with chest trauma. Hospital length of stays, time to ambulation, a patient satisfaction survey, incentive spirometry, forced vital capacity measurements, and the injury severity score will be correlated to a control group to determine its' effectiveness. The quantitative data points will be collected over the first three days of hospital stay and 24 hours prior to discharge. The qualitative data will be collected prior to patient discharge. The hypothesis of this study is that the use of the Duracore splinting device will reduce hospital length of stays and improve patient lung capacities over the course of admission following chest trauma.

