Variables to be collected are:

- Age (years)
- Gender
- Diagnosis

CHI Institute for Research and Innovation

- Incentive Spirometry values for this admission
- FVC/FEV1 values for this admission
- Height, Weight, and Ethnicity for FVC/FEV₁ % predicted calculation
- Averages from the patient satisfaction survey using a Likert Scale
- Length of Stays
- Time to Ambulation
- Injury Severity Score

10) Procedures Involved

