The design of this study is a randomized experimental trial. The procedures involved in this study will first include obtaining the individual's consent to participate. Incentive spirometry is a standard of care that has been proven to improve deep breathing for patients. FVC/FEV₁ measurements are not always routinely done at this site but has been proven to be an indicator in respiratory deterioration in this population. Enrollment of each subject will be on a one to one basis for control and experimental groups. The trial will be randomized to reduce bias by randomly selecting patients between control and experimental groups by alternating every other patient receiving the treatment. Height, sex, ethnicity, and age will be accounted for as well to calculate the percent predicted FVC/FEV_1 to reduce statistical error. Enrollment will be based on patient consent. After enrollment into the study after admission to the hospital, baseline values of incentive spirometry (IS) and spirometry will be done. The patient will then be placed in the experimental or control group after being assigned a group via envelope randomization. If the patient is under experimental, they will receive a splinting device for treatment. Control groups will receive standard of care treatment without the splinting device. Continued analysis of IS and FVC/FEV₁ will occur over three days, and a final collection prior to discharge. Discharge planning will be coordinated with respiratory therapy, so the patient does not go home without completing the survey and final analysis. The patient satisfaction survey will be a paper survey administered to the patient. Patient identifying information will not be present on this form to maintain confidentiality. The patient will be asked if they would like to complete the form and that it is an anonymous short survey to help with identifying how the patient felt about the research. The subject will only be enrolled in the study for the duration of their hospital stay as an inpatient. There will be no follow-up after discharge, and any patients who are discharged without completing the final analysis will be omitted from the study.

11) Data Analysis Plan

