Data analysis will include a two-tailed t-test to account for significance between control and experimental groups. This will be done with both incentive spirometry and FVC/FEV₁. Correlations will be made with time to ambulation and length of stays, as well as injury severity score. Graphic representation of trends will also be used to demonstrate differences between the groups. Qualitative analysis will include providing averages from the questionnaire using a Likert scale. These averages will be used to determine whether the population felt the device provided any help with their chest trauma. Number of subjects was based on a power analysis

using FVC/FEV₁ as the primary variable. Previous literature suggests a standard deviation of approximately 0.20-0.60 for FVC/FEV₁ values. SD was set at 0.40. Unilateral control was estimated to be 50% of predicted values (FVC/FEV₁) due to the nature of the injury, set at approximately 1.50L, with bilateral set at approximately 1.35L. Unilateral experimental group means were increased by 20% of predicted values to 1.80L, and bilateral to 1.50L. The required sample size to achieve 80% power to detect difference between splint and control groups is 104, with each group requiring 26 subjects each. Power calculations were performed in R version 4.0.0 with the pwr2ppl package, using the anova2x2 function. Number of subjects to be used are 150 to account for withdrawals, incomplete data sets, extraneous results, etc. This is a single site study.

Patient satisfaction surveys will use a numbered Likert Scale. The averages of each answer will be used to reinforce the efficacy of the device and correlate to primary data. Randomization will occur by experimenter-blinded envelope randomization.

12) Provisions to Monitor the Data to Ensure the Safety of Subjects

Subjects will be monitored for the duration of their stay by all staff members, and any adverse events related to the device itself will be reported accordingly. This device claims minimal risk to patients due to its unrestrictive and non-invasive nature but will be monitored by investigators for any adverse effects. **The Data Safety Monitoring staff will review all documentation accordingly at least quarterly.**

13) Withdrawal of Subjects

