splinting device is to be non-significant device. It is low risk and does not present potential for serious risk to the health, safety, or welfare of a subject. FDA recommendations are being followed to label the device accordingly. A nonsignificant risk device study requires only IRB approval prior to initiation of a clinical study. Sponsors of studies involving nonsignificant risk devices are not required to submit an IDE application to the FDA for approval per FDA regulations. The plan is to comply with the abbreviated IDE requirements under §812.2 (b):

The device will be labeled with "CAUTION – Investigational Device.
Limited by Federal (or United States) law to investigational use."
This is the current label for the device

• Will monitor for any adverse effects daily with subjects using the device 33) Other Requirements

REGULATORY, ETHICAL AND LEGAL OBLIGATIONS

Institutional Review Boards/Ethics Committees

• Before implementing this study, the protocol and all associated documents must be reviewed by a properly constituted committee or committees responsible for approving clinical studies. The IRB's written, signed approval letter must contain approval of the designated investigator(s) and the protocol (identifying protocol title, date and version number).

• Any change or addition to the protocol can only be made in a written protocol amendment that must be approved by the responsible party and the local IRB.

Patient Confidentiality and Disclosure

• Data on patients collected on eCRFs during the trial will be documented in an anonymous fashion and the patient will only be identified by the patient enrollment number, and by his/her initials. If, as an exception, it is necessary for regulatory reasons to identify the patient, all parties are bound to keep this information confidential.

• The investigator will guarantee that all persons involved will respect the confidentiality of any information concerning the study patients. All parties involved in the study will maintain strict confidentiality to assure that neither the person nor the family privacy of a patient participating in the trial is violated. Likewise, the appropriate measures shall be taken to prevent access of non-authorized persons to the study data.

Collection, Monitoring and Auditing Study Documentation, and Storage

Collection of Data and Monitoring Procedures

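### Adverse events are not collected the same way in both arms, so any safety statement from the trial would have no concurrent control rate

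*Combined protocol and SAP*

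**What the plan says.** Safety is covered in three places.

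- **Section 12 (Provisions to Monitor the Data to Ensure the Safety of Subjects)** covers everyone in general terms: "Subjects will be monitored for the duration of their stay by all staff members". Its reporting commitment is narrower: "any adverse events related to the device itself will be reported accordingly". It then says of the device that it carries minimal risk "but will be monitored by investigators for any adverse effects". Data safety monitoring staff review the documentation at least quarterly.
- **Section 26 (Drugs or Devices)** lists, under the abbreviated IDE requirements, the one check with a stated frequency: "Will monitor for any adverse effects daily with subjects using the device".
- **Section 14 (Risks to Subjects)** gives two possible device risks, discomfort and allergy to the fabric. It also says that the fractures may cause discomfort and pain during the breathing tests.

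The control arm has no device: "Control groups will receive standard of care treatment without the splinting device" (Section 10).

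The data sections contain no safety item. In Section 9 the list headed "Variables to be collected are" has ten bullets, from age to Injury Severity Score, and none is an adverse event or complication. The outcomes that "will be correlated to a control group to determine its' effectiveness" are length of stay, time to ambulation, the survey, incentive spirometry, forced vital capacity and injury severity. Section 11 plans a two-tailed t-test ("This will be done with both incentive spirometry and FVC/FEV₁"), correlations and survey averages.

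**The concern.** Two filters act together. The scheduled check looks for events in one arm only, and the reporting rule admits only events attributed to the device. A control patient's event passes neither, and there is no field to hold it.

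What is at stake is how any event in a splint patient can be interpreted. Discomfort is both a named device risk and an expected result of the injury. Section 10 likewise treats respiratory deterioration as something that happens in this population. If a splint patient has either, someone must decide case by case whether the splint was responsible. The randomised control arm could show how often the same event happens without a splint, but only if it is counted there with the same effort. More intensive checking in one arm also biases a later comparison, since more events are found where more are sought.

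**Working it through.** **1. Can a control event reach the dataset?**

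| Step | Splint arm | Control arm | Source |
|---|---|---|---|
| General staff monitoring | Yes | Yes | Section 12 |
| Scheduled daily check | Yes | None stated | Section 26 |
| Investigator monitoring for adverse effects | Yes, tied to the device | None stated | Section 12 |
| Reporting rule | Device-related events | Cannot apply, no device | Sections 10, 12 |
| Event among collected variables | No | No | Section 9 |
| Event analysis | No | No | Section 11 |

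The arms match only at the first step, which has no form, event definition or schedule. At the next three the plan provides for splint users alone. At the last two neither arm has anything.

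**2. Arm sizes.** The documents give no safety figure to reproduce, so the arm sizes come from the sample size in Section 6.

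- Control mean (1.50 + 1.35)/2 = 1.425; splint mean (1.80 + 1.50)/2 = 1.65; difference 0.225; SD 0.40; two-sided alpha 0.05 (assumed, since none is stated).
- For the treatment main effect in a 2×2 ANOVA with n per cell, the noncentrality is n × 0.225²/0.40². At n = 26 it is 8.23 on 1 and 100 degrees of freedom, giving 81.1% power. At n = 25 power is 79.5%.
- So 26 per cell, 104 in total, reproduces. That is 52 per arm; the enrolment target of 150 gives 75 per arm.

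**3. What one-arm data can say.**

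- If no event is seen in n splint patients, the one-sided 95% upper bound is 1 − 0.05^(1/n): 5.6% for n = 52 and 3.9% for n = 75.
- The chance of seeing at least one event at true rate p is 1 − (1 − p)^n. For p = 1%, 2% and 5% it is 41%, 65% and 93% with 52 patients, and 53%, 78% and 98% with 75.

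**4. What a two-arm comparison could say.** The documents give no background event rate, so the control rate is assumed and a range is shown. The detectable rate uses the normal approximation for two proportions (pooled variance under the null, 80% power, two-sided 0.05). The half-width is 1.96 × √(2p(1 − p)/n), with both arms at the control rate p.

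| Assumed control rate | Detectable splint rate, 52 / 75 per arm | 95% CI half-width for the difference in percentage points, 52 / 75 per arm |
|---|---|---|
| 5% | 24% / 20% | 8.4 / 7.0 |
| 10% | 32% / 28% | 11.5 / 9.6 |
| 20% | 46% / 41% | 15.4 / 12.8 |

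Only a large excess would be detected. The gain is an unbiased descriptive comparison, not a test of safety.

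**The case against.** The case for leaving the plan alone has several parts.

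- **Controls are watched.** Section 12 has all staff monitoring all subjects throughout the stay. The Retention of Documents text requires source records holding all medical information for each patient, and the quarterly review is not limited to splint users. This stands as far as it goes: it would be wrong to infer that controls are unmonitored or that their events would be lost. A serious event would probably be in the chart. But nothing directs anyone to extract it, and later retrieval depends on what staff happened to note.
- **No safety conclusion is planned.** Correct. Safety is not an objective, endpoint or analysis, and the low-risk statements in Sections 14 and 26 are prior assertions about the device. The daily-check bullet is a regulatory commitment. The point concerns only a safety statement that the report might make; a combined clinical and statistical report and a publication are both promised.
- **The control arm is already used.** Spirometry and length of stay are compared between arms, and a splint that impaired breathing might show there. This stands, so the control arm is not wasted. However, these measures are not events, and Section 13 allows withdrawal for deterioration, which weakens the signal.
- **A fabric allergy needs no control rate.** Largely true. It does not help with discomfort.
- **Relatedness.** A reader might infer that unblinded investigators judge it. The documents do not say who does, and Sections 3 and 11 describe the experimenters as blinded. A check confined to splint users is hard to square with that, but this is an inference and the point does not depend on it.
- **Small numbers.** This stands and limits the claim to description.

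**Conclusion.** The point holds in this form: event ascertainment differs by arm, and followed as written the plan yields safety data from splint users only, filtered by judged relatedness. Any safety statement would have no concurrent control rate.

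The asymmetry rests on the text alone. The 5.6% and 3.9% bounds assume zero observed events and 52 or 75 evaluable splint patients. The detectable rates (about 20% to 24% at a 5% control rate) assume that control rate, alpha 0.05 and equal arms. None of this shows that the splint is harmful or that the efficacy result is at risk. It is an inexpensive improvement worth making before enrolment is far advanced, because events not recorded evenly at the time are hard to recover evenly afterwards.

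**What to change.** Reconcile Sections 9, 12 and 26, and add one line to Section 11:

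1. **Section 9:** add one short, defined list of adverse events and respiratory complications, including the discomfort and fabric reaction named in Section 14.
2. **Sections 12 and 26:** abstract that list from the chart on the same schedule in both arms, whatever the judged relation to the device. Record relatedness in a separate field, with the assessor's role stated. If the daily check of splint users continues alongside, mark events found only through it, so that the between-arm table rests on a source common to both arms.
3. **Section 11:** tabulate events by randomised arm, with confidence intervals for each rate and for the difference, for the quarterly review and the final report. Label the comparison descriptive. Count all randomised patients, including those withdrawn or discharged before the final assessment, subject to any request by a patient on use of their data.

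**Cost.** A few form fields and some added chart abstraction. Study data are now collected at baseline, over three days and in the 24 hours before discharge, so a daily schedule would mean new work for control patients with longer stays. Section 18 allows only investigators to collect chart data, so it falls on them. No new procedures are needed, and the efficacy sample size and analysis do not change.
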